4.2.1.6 Sensitivity Analyses of the Primary Immunogenicity Endpoint

Sensitivity analyses of the primary endpoint are not currently planned.

4.2.1.7 Supplementary Analyses of the Primary Immunogenicity Endpoint

4.2.1.8 Supplementary analyses of the primary endpoint are not currently planned. Subgroup Analyses

Descriptive summaries of GMCs, GMFRs, and seroresponse rate will be reported for the following subgroups:

- Age group categories (60 to 69, 70 to 79, and ≥ 80 years of age)
- Tertiles of baseline RSV A nAb concentration ($\leq 33.3\%$, $> 33.3\%$ to $\leq 66.7\%$, $> 66.7\%$ across vaccination groups)

For each subgroup variable, if an adequate number of participants in each subgroup category is available to allow convergence of the model, model-adjusted GMCs will be derived for each subgroup category using the same ANCOVA and MMRM models as described above. Higher order interaction terms (ie study group*subgroup for ANCOVA model or visit*study group*subgroup for MMRM model) will be included in the model, using an appropriate

covariance matrix. If model convergence is not achieved, each subgroup level will be analyzed separately using a common, simpler model without the higher order interactions.

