3.4.1 General Study Level Definitions

Baseline

Baseline for immunogenicity endpoints is defined as the last non-missing result on the day of receiving study vaccination. Samples taken on the day of vaccination will be considered as evaluable for baseline, regardless of whether samples were drawn post-vaccination. If there is no value prior to or on the day of study vaccination, the baseline value will not be imputed and will be set to missing.

Baseline Tertiles

Baseline tertiles are defined as follows: first tertile is $\leq 33.3^{\text{rd}}$ percentile, second tertile is $> 33.3^{\text{rd}} - \leq 66.7^{\text{th}}$ percentile, and third tertile is $> 66.7^{\text{th}}$ percentile. Tertiles will be derived for each neutralization assay, across both study groups.

Study Groups

For the primary and final analyses, the study groups will be displayed in summaries as follows:

- IVX-A12 (RSV + hMPV)
- AREXVY (RSV)

Study Day

Study Day is defined as (date of assessment – date of study vaccination) + 1. Thus, the day of study vaccination will be study Day 1. There is no study Day 0.

Geometric Mean Concentration/Titer

Geometric mean concentrations/titers (GMCs/GMTs) will be calculated as the anti-logarithm $\Sigma(\log_2 \text{transformed response}/n)$, ie, as the anti-logarithm transformation of the mean of the

log₂-transformed response, where n is the number of participants with non-missing response information.

The CI for the GMC/GMT is calculated as the anti-logarithm transformation of the upper and lower limits of the two-sided 95% CI for the mean of the log₂-transformed responses.

Geometric Mean Concentration/Titer Ratio

The GMC/GMT ratio will be calculated as the geometric mean of the post-baseline response for IVX-A12 divided by the geometric mean of the post-baseline titer for AREXVY. The denominator for each geometric mean response is the number of participants with non-missing post-baseline response information.

The CI for the GMC/GMT ratio is calculated as the anti-logarithm transformation of the upper and lower limits of the two-sided 95% CI for the difference in means of the log₂-transformed responses.

Geometric Mean Fold Rise

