4.2.1.5 Primary Analysis of Primary Immunogenicity Endpoint

For the Day 29 primary analysis model-adjusted GMCs, along with their corresponding 95% CIs, will be estimated using an analysis of covariance (ANCOVA) model that includes a continuous dependent variable of log 2 response at Day 29, study group as a fixed effect (factor), and log 2 baseline response (continuous) and age group (categorical; 60 to 69, 70 to 79, and ≥ 80 years of age) as covariates.

Least square means and 95% CIs will be back-transformed to provide Day 29 model-adjusted GMCs and CIs for each study arm.

The following plots will be created for the Day 29 analysis:

- A bar plot by study group showing the GMCs and 95% CIs at baseline (raw values) and Day 29 (adjusted values)
- A line plot by study group showing the GMCs and 95% CIs at baseline (raw values) and Day 29 (adjusted values)
- A boxplot with scatterplot overlay by study group showing the distribution of the raw concentration data at Day 29
- A reverse cumulative distribution plot of the fold rise at Day 29, with fold rise values displayed on the x-axis and the percentage of participants with fold rise values greater than or equal to the corresponding fold rise displayed on the y-axis

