4.2.3.2 Exploratory analyses of the exploratory endpoints

To evaluate durability of nAb responses post-vaccination, model-adjusted GMCs/GMTs at Days 29 and 181, along with their corresponding 95% CIs, will be estimated using a mixed model for repeated measures (MMRM) that includes a dependent variable of log 2 responses, study group as a fixed effect, log 2 baseline response, age group, visit indicators (Days 29 and 181) as covariates, and a study group by visit interaction term. An appropriate covariance matrix structure will be selected to address repeated measurements. Least square means and 95% CIs will be back-transformed to provide model-adjusted GMC/GMTs and confidence intervals by study group, for each follow-up visit, Days 29 and 181. Unadjusted GMCs/GMTs, GMFRs from baseline, and seroresponse rate, with corresponding 95% CIs, will be estimated for each study group and summarized by post-baseline visit. Plots described in Section 4.2.1.5 may be repeated for these analyses.

Multiple imputation techniques will not be applied for any missing post-baseline immunogenicity measurement. This is because the MMRM inherently accounts for the missingness, under the assumption that the missing data are missing at random (MAR). Thus considering that missing data are MAR is a reasonable assumption for this descriptive clinical trial, then it is not necessary to perform MI.

To compare nAb response between IVX-A12 and the AREXVY, the GMC/GMT ratio and difference in seroresponse rate, along with corresponding 95% CIs, will be estimated and summarized at Day 29 and Day 181. The difference in seroresponse rate will be unadjusted and the 95% CIs calculated based on the Miettinen-Nurminen method (Miettinen and Nurminen 1985). Unadjusted and model-adjusted (from MMRM above) GMTRs with 95% CIs will be calculated.

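### Adjusted GMCs for baseline-tertile subgroups keep continuous baseline in the model with no stated reference value; default least-squares means would place the outer tertiles at a baseline outside those tertiles

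*SAP*

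**What the plan says.** The Day 29 ANCOVA in SAP 4.2.1.5 has "study group as a fixed effect (factor), and log 2 baseline response (continuous) and age group" as its terms, and "Least square means and 95% CIs will be back-transformed to provide Day 29 model-adjusted GMCs and CIs for each study arm". The MMRM in SAP 4.2.3.2 has "log 2 baseline response, age group, visit indicators (Days 29 and 181) as covariates, and a study group by visit interaction term", and its LS means are back-transformed in the same way.

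SAP 4.2.1.8 lists two subgroup variables: age group and "Tertiles of baseline RSV A nAb concentration". SAP 3.4.1 adds that "Tertiles will be derived for each neutralization assay, across both study groups". Two kinds of output are planned:

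- Unadjusted output, without condition: "Descriptive summaries of GMCs, GMFRs, and seroresponse rate will be reported for the following subgroups".
- Adjusted output, if numbers allow the model to converge: "model-adjusted GMCs will be derived for each subgroup category using the same ANCOVA and MMRM models as described above". A study group by subgroup term is added to the ANCOVA, and a visit by study group by subgroup term to the MMRM. If the model does not converge, "each subgroup level will be analyzed separately using a common, simpler model without the higher order interactions".

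Nothing in the SAP or protocol removes continuous baseline when the subgroup is itself a baseline tertile, or states the baseline value at which LS means are computed. SAP 4.2.3.3 allows the same subgroup analyses to be repeated for the exploratory endpoints.

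**The concern.** Tertile summaries are meant to show how the response varies with pre-existing antibody. If continuous baseline stays in the model and LS means are taken at the overall mean, each tertile's adjusted GMC is moved along the fitted slope to one common baseline. For the outer tertiles no participant has that baseline. A table labelled by tertile could then show nearly equal adjusted GMCs beside unadjusted GMCs that differ several-fold. A reader could wrongly conclude that baseline hardly matters.

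The fallback makes the label ambiguous. A model fitted within one tertile gives LS means at that tertile's own baseline level, whether or not the unlisted simpler model keeps the covariate. The quantity reported would therefore depend on whether the joint model converged. This bears mainly on the MMRM, because the Day 29 ANCOVA is a closed-form fit.

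Protocol 4.2 says the study should help refine assumptions for possible Phase 3 endpoints, so tertile-specific levels may well be read.

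**Working it through.** **1. SD from SAP Table 1.** The stated SD is redacted, so it is back-solved as SD = (half-width of the log2 CI) / [t(0.975, N−2) × √(4/N)]. For N = 140 and ratio 0.9, the half-width is log2(1.42/0.57)/2 = 0.658, and SD = 0.658 / (1.977 × 0.169) = 1.97 log2. The six 95% intervals give 1.97 to 1.985. One such SD reproduces 0.57 to 1.42 and 23 of the 24 limits in Table 1; the other differs by 0.01. This checks consistency only, since the SD comes from the same table.

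**2. Where the overall mean lies.** For a normal log2 baseline the tertile cut points are at ±0.431 SD and the outer-tertile means at ±φ(0.431)/(1/3) = ±1.091 SD. The overall mean is therefore in the middle tertile, and it was so in essentially all simulated trials of 140. With skewed log2 values it falls at the 57th percentile (skewness 1) or the 63rd (skewness 2). It leaves the middle tertile only under extreme skew (69th percentile at skewness about 6).

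**3. What the LS mean reports.** Leaving age aside, the LS mean for group g and tertile t at baseline x₀ is (cell mean) + b × (x₀ − cell mean baseline). If the true effect is log-linear with slope b, setting x₀ to the overall mean gives the same value for every tertile within a group. The gradient removed, in log2, is 2 × 1.091 × ρ × 1.97, where ρ is the baseline-to-Day 29 correlation. For ρ = 0.5 this is 2.149, and 2^2.149 = 4.43.

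Simulation of the Day 29 ANCOVA: 1500 trials per setting, 70 per arm, pooled tertiles, group ratio 0.9, six group-by-tertile cells plus one baseline slope, age omitted. T1 is the lowest tertile and T3 the highest.

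| ρ (assumed) | T3/T1, closed form | T3/T1 at own tertile mean | T3/T1 at overall mean | T1 GMC, reported ÷ own | T3 GMC, reported ÷ own |
|---|---|---|---|---|---|
| 0.1 | 1.35 | 1.34 | 0.98 | 1.17 | 0.85 |
| 0.3 | 2.44 | 2.46 | 0.99 | 1.58 | 0.63 |
| 0.5 | 4.43 | 4.35 | 1.00 | 2.09 | 0.48 |
| 0.7 | 8.05 | 7.83 | 1.00 | 2.79 | 0.36 |

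With age group in the model, own-tertile ratios of 1.34 / 2.39 / 4.38 / 7.90 are reported as 0.98 to 0.99. If 1.97 is a residual rather than a total SD, the closed-form ratios become 1.35 / 2.55 / 5.6 / 18.5, still reported as about 1.0.

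A second parameterisation, with age group included, assumed a baseline SD of 1.0 to 1.5 log2 and a slope of 0.3 to 0.7. It puts the lowest-tertile GMC 1.26 to 2.17 times too high and the highest at 0.79 to 0.46 of its own-tertile value. For SD 1.5 and slope 0.5, the three tertiles read 4017 / 4024 / 4150 at the overall mean and 2312 / 4025 / 7208 at the tertile means (arbitrary scale).

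**4. Precision.** With about 23.3 participants per cell, the variance factor at the tertile's own mean is 1/23.3 = 0.0429. The within-tertile baseline variance is 1 − (2/3) × 1.091² = 0.207 SD², so moving to the overall mean adds 1.091² / (140 × 0.207) = 0.041. The SE ratio is √[(0.0429 + 0.041)/0.0429] = 1.4.

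**5. MMRM and its fallback.** Simulation: 250 trials per setting, unstructured covariance, one baseline slope; residual correlation 0.7 and 10% missing at Day 181 are assumed; Monte Carlo SE at most 0.055 log2. At ρ = 0.3 / 0.5 / 0.7 the joint model gives T3/T1 of 0.97 / 0.98 / 1.00 at Day 29 and 0.95 / 0.98 / 1.00 at Day 181. Separate tertile models give 2.5 / 4.4 / 7.8 and 2.4 / 4.4 / 7.8.

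**6. Other shapes.** ANCOVA at ρ = 0.5, with z the standardised log2 baseline:

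- effect flat above the mean: 4.4 reported as 1.0
- tanh(z): 5.1 reported as 2.1
- tanh(2z): 5.5 reported as about 3.0
- step at the mean: 5.5 reported as about 3.0

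The gradient is removed or weakened, depending on shape.

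**7. What does not change.** The model has no group-by-baseline term, so the within-tertile vaccine ratio is the same at any reference baseline. It stayed at the simulated 0.9.

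**The case against.** The strongest reply concerns weight. The study tests no hypothesis (protocol 9.1), and no decision uses these values. The unadjusted tertile GMCs, GMFRs and seroresponse rates are planned regardless and already show the real gradient. Adjusted GMCs at each tertile's own mean would nearly duplicate the unadjusted ones (T3/T1 within about 0.01 in the simulations). A mean at a common baseline is also a legitimate quantity, and the SAP never says that default LS means will be used; the reference value could be set in the table specifications. Non-convergence looks unlikely with about 47 participants per tertile (140/3). Finally, the size rests on a correlation that the documents do not give; at 0.1 the outer-tertile shift is only about 1.17-fold.

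Most of this stands, and it makes the point minor. It does not remove it. Running the stated model with ordinary LS means produces extrapolated outer-tertile values under a label that presents them as tertile results. If a common baseline is intended, the SAP should say so and give the value. The direction of the shift needs only a positive slope; the correlation sets its size.

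**Conclusion.** The point holds, conditional on ordinary LS means being used. SAP 4.2.1.8 as written would then report outer-tertile adjusted GMCs at a baseline outside those tertiles. The T3/T1 gradient would be flattened to about 1.0 under a log-linear effect and flattened or weakened under the other shapes tried. The fallback would report a different quantity under the same label.

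The assumptions are a log2 baseline without extreme skew, a positive relation with the Day 29 response, and, for the size only, the SD implied by Table 1 and the assumed correlations. The consequence is confined to the levels of a conditional, descriptive subgroup output. It could carry over to RSV B and hMPV A/B if SAP 4.2.3.3 is exercised. It is worth correcting because the correction is cheap.

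**What to change.** Add to SAP 4.2.1.8, and so by reference to 4.2.3.3: *For baseline-tertile subgroups, least-squares means will be evaluated at each tertile's own pooled mean log2 baseline, the same value for both groups, footnoted in the table.* In the simulations this recovers the gradient (4.35 at correlation 0.5, log-linear) and agrees with the separate-model fallback.

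Two alternatives also work. Continuous baseline can be omitted from the tertile model, which gives the same point gradient. Or unadjusted GMCs can be reported by tertile with adjusted ratios only.

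The cost is one SAP sentence, one AT option on the LSMEANS statement and one footnote, with no new data and no change to the primary analysis. The price is that adjusted GMCs are no longer at a common baseline across tertiles and will lie close to the unadjusted values. What adjustment then adds is correction for chance baseline and age imbalance between groups within a tertile.

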4.2.2 Primary Safety Endpoint

The primary safety objective is to assess the safety of single IM vaccination with IVX-A12 or AREXVY. All safety analyses are described in Section 4.6.

4.2.3 Exploratory Immunogenicity Endpoints: RSV A and RSV B nAb concentrations, and hMPV A and hMPV B nAb titers, through Day 181

4.2.3.1 Analysis considerations

The definition and derivation of summary quantities, as well as the handling intercurrent events, will be the same as the Primary Immunogenicity Endpoint described in Section 4.2.1. For summaries, evaluable participants will be those in the IAS with a non-missing value at both baseline and at least one non-missing post-baseline visit. Analyses below will be repeated for each of the four endpoints.

4.2.3.2 Exploratory analyses of the exploratory endpoints

To evaluate durability of nAb responses post-vaccination, model-adjusted GMCs/GMTs at Days 29 and 181, along with their corresponding 95% CIs, will be estimated using a mixed model for repeated measures (MMRM) that includes a dependent variable of log 2 responses, study group as a fixed effect, log 2 baseline response, age group, visit indicators (Days 29 and 181) as covariates, and a study group by visit interaction term. An appropriate covariance matrix structure will be selected to address repeated measurements. Least square means and 95% CIs will be back-transformed to provide model-adjusted GMC/GMTs and confidence intervals by study group, for each follow-up visit, Days 29 and 181. Unadjusted GMCs/GMTs, GMFRs from baseline, and seroresponse rate, with corresponding 95% CIs, will be estimated for each study group and summarized by post-baseline visit. Plots described in Section 4.2.1.5 may be repeated for these analyses.

Multiple imputation techniques will not be applied for any missing post-baseline immunogenicity measurement. This is because the MMRM inherently accounts for the missingness, under the assumption that the missing data are missing at random (MAR). Thus considering that missing data are MAR is a reasonable assumption for this descriptive clinical trial, then it is not necessary to perform MI.

To compare nAb response between IVX-A12 and the AREXVY, the GMC/GMT ratio and difference in seroresponse rate, along with corresponding 95% CIs, will be estimated and summarized at Day 29 and Day 181. The difference in seroresponse rate will be unadjusted and the 95% CIs calculated based on the Miettinen-Nurminen method (Miettinen and Nurminen 1985). Unadjusted and model-adjusted (from MMRM above) GMTRs with 95% CIs will be calculated.

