9.4.2 Immunogenicity

9.4.2.1 Primary and Secondary Endpoint(s)

Geometric mean titer (GMT) will be calculated as the anti-logarithm $\Sigma(\log_2 \text{transformed titer})/n$, ie, as the anti-logarithm transformation of the mean of the log-transformed titer, where n is the number of participants with titer information. The 95% CI about the GMT will be calculated as the anti-logarithm transformation of the upper and lower limits for a two-sided CI for the mean of the log-transformed titers.

The fold rise is calculated as the ratio of the post-dose titer level to the pre-dose titer level.

Geometric mean fold rise (GMFR) will be calculated as anti-logarithm of $\Sigma(\log_2$ transformed (post-dose titer/ pre-dose titer)/n. The 95% CIs for GMFR will be calculated similarly to those for GMT.

Seroresponse is a binary outcome where a success is when the fold rise in titers compared to baseline is ≥ 4 . The number and percentage of participants with post-vaccination seroresponse, and 95% CIs, calculated using the Clopper-Pearson exact method, will be provided. In the event of a 0% or 100% seroresponse, a one-sided 97.5% CI will be reported.

For the Day 29 primary analysis, adjusted GMTs and GMT ratios, along with their corresponding 95% CIs, will be estimated using an analysis of covariance (ANCOVA) model that includes a dependent variable of log titers, study arm as a fixed effect, and log baseline titer and age group as covariates. For the final analysis, model-adjusted GMTs and GMT ratios at Days 29 and 181, along with their corresponding 95% CIs, will be estimated using an mixed model for repeated measures (MMRM) that includes a dependent variable of log titers, study arm as a fixed effect, log baseline titer, age group (60 to 69, 70 to 79, and ≥ 80 years of age), visit indicators (Days 29 and 181) as covariates, and a study arm by visit interaction term.

Model-adjusted GMTs and GMT ratios will be used for analyses of the nAb response endpoints, while raw unadjusted values will be summarized as supportive analyses. GMFR and seroresponse will be unadjusted.

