2 CHANGES TO PROTOCOL PLANNED ANALYSES

The description for the Immunogenicity analysis set is further specified to target the intended study population.

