3.4 General Considerations

Data will be provided in data listings sorted by vaccination group and participant number. Tabular summaries will be presented by vaccination group and overall. Vaccination group will be defined as the actual vaccination received by a randomized participant.

Categorical variables will be summarized using frequency and percentages, where the denominator for calculation is the underlying analysis set population, unless otherwise stated. Continuous variables will be summarized with descriptive statistics of number of available observations, mean, standard deviation, median, minimum, maximum, and quartiles where appropriate.

All point estimates will be presented with a two-sided 95% CI, unless otherwise stated. For subgroup analyses, CIs will be presented for subgroup categories which have at least 5 evaluable participants per vaccination group.

The RSV nAb responses are measured as concentrations in IU/mL and therefore the geometric mean responses will be referred to as GMCs while the hMPV nAb responses are measured as titers (1/dilution) and the geometric mean responses will be referred to as GMTs. The GMCs and GMTs are referred to generally as geometric mean responses.

Immunogenicity summaries involving the Day 29 endpoint will include participants in the immunogenicity analysis set with a non-missing baseline and a non-missing result at Day 29.

For immunogenicity summaries involving data through Day 181, evaluable participants will be those in the immunogenicity analysis set with non-missing baseline and at least one non-missing post-baseline (Day 29 or 181) result.

Immunogenicity results below the LLoQ will be imputed to half of the LLoQ and results above the ULoQ will be imputed to the ULoQ prior to computing geometric mean responses. Responses will be imputed before any model-adjustment is performed.

The data analyses will be conducted using the SAS® System version 9.4 or above (SAS Institute Inc., Cary, NC). All SAS® programs used to generate analytical results will be developed and validated according to AstraZeneca programming standards and validation procedures.

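### The exploratory MMRM fits one log2 baseline slope to both Day 29 and Day 181; a baseline-by-visit term would be a cheap, minor improvement

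*SAP*

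**What the plan says.** SAP 4.2.3.2 models log2 response at Days 29 and 181 for RSV A, RSV B, hMPV A and hMPV B. Besides study group, the mean model has "log 2 baseline response, age group, visit indicators (Days 29 and 181) as covariates, and a study group by visit interaction term". Protocol 9.4.2.1 gives the same terms, ending in "visit indicators (Days 29 and 181) as covariates, and a study arm by visit interaction term", and the protocol synopsis agrees. No document puts a baseline-by-visit or age-by-visit term in this main model. The covariance is left open: "An appropriate covariance matrix structure will be selected to address repeated measurements".

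The MMRM is the source of the adjusted group comparison at both visits: "Unadjusted and model-adjusted (from MMRM above) GMTRs with 95% CIs will be calculated".

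The primary RSV A analysis is a separate ANCOVA on Day 29 alone (SAP 4.2.1.5), with its own baseline slope and age effect. Protocol 9.4.2.1 states that at that analysis "adjusted GMTs and GMT ratios, along with their corresponding 95% CIs, will be estimated using an analysis of covariance (ANCOVA) model". SAP Section 2 lists one departure from the protocol, which concerns the analysis set: "The description for the Immunogenicity analysis set is further specified to target the intended study population". The MMRM is therefore unchanged from the protocol.

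**The concern.** How strongly a titer depends on its pre-vaccination value may differ between 4 weeks and 6 months. A model with one slope for both visits then fits a compromise, and each visit's group contrast is corrected for chance baseline imbalance with a slope that is somewhat off.

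Two things are at stake, both small. First, RSV A can acquire two adjusted Day 29 ratios, one from the ANCOVA and one from the MMRM, that differ although no Day 29 value has changed. Second, the durability contrast at Day 181 carries some avoidable noise.

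**Working it through.** **1. The plan's own precision figure.** SAP 3.1 gives a 95% CI of 0.57 to 1.42 for a ratio of 0.9 with 140 participants; the SD is redacted. The half-width is log2(1.42/0.57)/2 = 0.658 log2. The implied SD is 0.658 / 1.96 / sqrt(4/140) = 1.99 log2 (about 1.38 on the natural-log scale). The six 95% intervals in SAP Table 1 give 1.98 to 2.01. With this SD, 23 of the table's 24 bounds are reproduced; the other (N = 180, ratio 0.9, upper 95% bound) computes to 1.35 against 1.34, a rounding-size gap.

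**2. The algebra.** Let d be the chance difference in mean log2 baseline between groups. Ignoring age and missing data:
- ANCOVA Day 29 log ratio = raw difference - (Day 29 slope) x d
- MMRM Day 29 log ratio = raw difference - (common slope) x d
- MMRM minus ANCOVA = (Day 29 slope - common slope) x d

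At Day 181 the shift is (Day 181 slope - common slope) x d. When the common slope lies between the two, the shifts have opposite signs. Randomization gives d an expectation of zero, so the average shift is about zero.

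**3. Hand check.** Assume a baseline SD of 1.5 log2. Then SD(d) = 1.5 x sqrt(2/70) = 0.254 log2. For slopes 0.4/0.7 with a midway common slope of 0.55, the slope is off by 0.15. One SD of d moves the log ratio by 0.15 x 0.254 = 0.038 log2, and the median shift is 0.674 x 0.038 = 0.026 log2, or 1.8%.

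**4. Simulation.** From the documents: 140 participants, 1:1, stratified by age, ratio 0.9, total SD 1.99 (back-calculated). Assumed: age mix 50/35/15%, baseline SD 1.5, 10% missing at Day 181, Day 29 complete, unstructured covariance. There were 800 trials per cell. Each cell below gives results for residual correlation 0.4, then 0.8. The gap is MMRM against ANCOVA at Day 29, as median (95th percentile).

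| Slopes Day 29/181 | SAP model, gap % | With baseline-by-visit, gap % | Day 29 SE, SAP model / by-visit terms |
|---|---|---|---|
| 0.5/0.5 | 0.38 (2.16); 0.22 (1.23) | 0.12 (0.55); 0.07 (0.31) | 0.999; 1.000 |
| 0.5/0.6 | 0.56 (2.94); 0.52 (2.57) | 0.12 (0.56); 0.08 (0.36) | 0.999; 1.000 |
| 0.4/0.7 | 1.84 (6.92); 2.38 (8.32) | 0.13 (0.62); 0.11 (0.48) | 1.007; 1.013 |
| 0.3/0.8 | 3.64 (12.61); 5.19 (17.87) | 0.15 (0.67); 0.13 (0.59) | 1.027; 1.054 |

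Against the planned half-width of 0.658 log2, the median gap for 0.4/0.7 is log2(1.0184)/0.658 = 4% to log2(1.0238)/0.658 = 5%. For 0.3/0.8 it is log2(1.0364)/0.658 = 8% to log2(1.0519)/0.658 = 11%.

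The Day 181 ratio shifts, against by-visit terms, by a median of 0.5-0.7% (equal slopes) to 1.6-2.5% (0.3/0.8). Its SE ratio is 0.998 to 1.017.

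**5. Validity.** The largest mean difference over all runs is 0.0051 log2. Day 29 coverage of the SAP model is 0.927 to 0.966.

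**6. Price of an unneeded term.** A second simulation (1,500 trials; baseline SD 1.3, residual SD 1.7, correlation 0.7) with slopes 0.5/0.5 gives a Day 181 SE of 0.2917 without the term and 0.2923 with it: 0.2923/0.2917 = 1.002. With slopes 0.3/0.7 the term lowers it from 0.2971 to 0.2934, or 1.2%; with residual SD 1.2, from 0.2128 to 0.2072, or 2.6%.

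**7. Sensitivity.** At correlation 0.6, reading 1.99 as a residual SD gives median gaps of 1.52% (0.4/0.7) and 2.73% (0.3/0.8). A baseline SD of 1.0 gives 1.07% and 1.90%. If 4% of Day 29 values are missing, equal slopes give 1.32% before and 1.05% after the added term at correlation 0.4, and 2.12% and 2.06% at 0.8. Slopes 0.3/0.8 give 3.95% to 1.11% and 6.00% to 2.20%.

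**The case against.** The sponsor can fairly say that this is a choice between two valid models. SAP and protocol agree, the endpoints are exploratory, nothing is tested, unadjusted summaries are reported alongside, and the primary ANCOVA is untouched. All of that stands, and it is why the point is minor.

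Nothing in the documents shows that the slopes differ. That also stands. At 0.5/0.5 and 0.5/0.6 there is no SE gain, and the larger gaps need slopes as far apart as 0.3 and 0.8. The runs use RSV A-type inputs; no SD is given for RSV B or hMPV. The algebra applies to all four endpoints, but the sizes may not.

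The SAP already lets effects vary by visit in its subgroup models (4.2.1.8), for age group and baseline tertile. This is only a partial answer: for these endpoints those analyses are optional (4.2.3.3), and they do not change the main model.

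The two Day 29 ratios may differ in any case, because SAP 4.2.1.1 requires a Day 29 value while 4.2.3.1 accepts any post-baseline value. That is right, and it limits what the added term can achieve.

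**Conclusion.** The point holds as a cheap improvement of minor weight. It is not an error in the plan. With Day 29 complete, the median Day 29 gap runs from 0.2-0.4% (equal slopes) through about 2% (0.4/0.7) to about 4-5% (0.3/0.8), with an SE penalty of 0% to about 5%. These sizes rest on assumed slopes, baseline SD, correlation, age mix and missingness.

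Four stronger readings are tempting and are not supported:
- **A reader might infer that the MMRM is biased.** Under randomization it is not, and coverage holds. In one run with 10% group-dependent loss at Day 181, missing at random, and unequal slopes, the Day 181 mean error was +0.016 log2 without the term and -0.006 with it (Monte Carlo SE about 0.006). That is about 1% on the ratio.
- **A reader might infer that it is always less precise.** That is so only if the slopes differ; otherwise it is marginally more precise.
- **A reader might infer that the shared age effect is an equal fault.** With baseline-by-visit alone and Day 29 complete, the remaining gap was at most 1.0% at the 95th percentile, including a run in which age effects differed by visit.
- **A reader might infer that the change makes the two Day 29 ratios identical.** It does not if Day 29 values are missing.

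**What to change.** In SAP 4.2.3.2, add a log2 baseline-by-visit term and name an unstructured 2x2 covariance (three parameters). Fix both in advance for all four endpoints. Record the change in SAP Section 2. For an exploratory analysis, no separate protocol amendment is needed.

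Leave the age effect common to both visits. Do not make an age-by-visit term conditional on observed stratum counts, since the model would then depend on the data. The SAP 3.4 rule "For subgroup analyses, CIs will be presented for subgroup categories which have at least 5 evaluable participants per vaccination group" governs the display of subgroup intervals, not the choice of model terms.

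The cost is one extra mean parameter per endpoint and about 0.2% in SE if the slopes are equal. No new data are needed and the primary ANCOVA is unchanged. Some difference from the ANCOVA remains if Day 29 values are missing, because the evaluable sets differ.
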